# 7.3.2 Circumstances for Unblinding

Blinding of study treatment assignment is critical to the integrity of this clinical study. However, in the event of a medical emergency in an individual participant or pregnancy of the partner of a male participant in which knowledge of the IP is critical to the participant's management, the blind for that participant may be broken by the investigator. The participant's safety takes priority over any other considerations in determining if a treatment assignment should be unblinded.

Before breaking the blind of an individual participant's treatment, the investigator should determine if the unblinded information is necessary (ie, that it will alter the participant's immediate management). In many cases, particularly when the emergency is clearly not related to the IP, or the problem may be properly managed by assuming that the participant is receiving the IP. It is highly desirable that the decision to unblind treatment assignment be discussed with the medical

Protocol Amendment No.: 05

monitor, but the investigator always has ultimate authority for the decision to unblind. The actual task of unblinding can be delegated by the investigator to a designee assigned the task on the Delegation of Authority. The Principal Investigator or appointed designee should only call in for emergency unblinding after the decision to unblind the participant has been documented.

In case of an emergency unblinding, the investigator(s) has unrestricted access to randomization information via the IRT system and is capable of breaking the blind through the IRT system without prior approval from the sponsor. Following the unblinding the investigator shall notify the medical monitor.

In cases of accidental unblinding, contact the medical monitor and ensure every attempt is made to minimize additional disclosure and the impact of unblinding.

Any request to unblind a participant for nonemergency purposes should be discussed with the medical monitor.

A scientist in the NonClinical Disposition and Bioanalysis department of BMS (and/or a designee in the external bioanalytical laboratory) will be unblinded to the randomized treatment assignments in order to minimize unnecessary bioanalytical analysis of samples. Any results shared by the NonClinical Disposition and Bioanalysis group with the Sponsor's study team will be blinded to ensure integrity of the study.

#### 7.4 Dosage Modification

## **Day 1 study visit:**

On Day 1, participants will not self-administer morning the dose; the dose will be administered at the site. Participants will remain at the site for at least 4 hours post dose. Orthostatic BP and HR will be performed predose and 1.5, 2, and 4 hours post dose.

Participants will not receive the Day 1 evening dose if any of the defined low BP criteria are met (refer to Day 1 BP monitoring in Section 5.1.2.1 for details).

If either *asymptomatic* or *symptomatic* low BP criteria are met, participants will not receive the Day 1 evening dose and will remain at the site until:

- a) The participant provides 2 consecutive seated BP measurements (at least 30 minutes apart) showing SBP > 85 mmHg and DBP > 55 mmHg
- b) The participant does not demonstrate orthostatic hypotension
- c) Potential symptoms of decreased BP (as described above) have not been present for at least 30 minutes

Participants will return to the site on Day 2 prior to receipt of the morning dose.

#### Day 2 study visit:

On Day 2, participants will be issued new kits/containers. Participants will not self-administer the morning dose; the dose will be administered at the site.

At the Day 2 visit, participants will receive a reduced dose. Those randomized to 30 mg or 60 mg BMS-986278 will have their medication kits/containers replaced with 10 mg BMS-986278. Those randomized to placebo will have their medication kits/containers replaced with the placebo for 10 mg BMS-986278. These participants will continue on 10 mg BMS-986278 BID or matching placebo for 10 mg BMS-986278 BID. All instances of dose reduction are communicated by the site or vendor to the central study team.

On Day 2, participants will remain at the site for at least 4 hours post dose. Orthostatic BP and HR will be performed predose and 1.5, 2, and 4 hours post dose. Participants will be carefully monitored for symptoms associated with low BP.

If either *asymptomatic* or *symptomatic* low BP criteria are met (refer to Day 1 BP monitoring in Section 5.1.2.1 for details), participants will be discontinued from study treatment (but continue in the study). All other participants will remain on reduced dose (10 mg BMS-986278 BID) or matching placebo for 10 mg BMS-986278 BID).

#### **Post-Day 1 study visits:**

At every post-Day 1 study visit, participants will not self-administer morning doses; doses will be administered at the site. Vital signs, including orthostatic assessments, will be performed at every post-Day 1 study visit.

If either asymptomatic or symptomatic low BP criteria are met (refer to Day 1 BP monitoring in Section 5.1.2.1 for details), participants will remain at the site for at least 4 hours post dose. Orthostatic BP and HR will be performed 1.5, 2, and 4 hours after the low BP criteria at predose are detected. Participants will be carefully monitored for symptoms associated with low BP. If a decision is made to reduce to 10 mg BMS-986278 BID (or placebo for 10 mg BMS-986278 BID), the participant will return to the site the following day prior to receipt of the morning dose. Dose reduction should be appropriately noted in the case report form.

Dose modification criteria described above will apply to the OTE.

Dosage modifications for other reasons are otherwise not permitted.

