Height and weight measurement	X	X					X			X		Height measured at screening only.
Laboratory/Saf	ety Assessm	ents										
12-lead ECG	X	X			X		X			X		All ECGs must be performed prior to bronchodilator administration OR at least 20 hours after bronchodilator administration. ECG on Day 1, Weeks 4 and 12 to be collected before morning dosing.  See Section 9.4.3 for further details.
Serial ECG for participants enrolled in intensive PK substudy			See notes.									Intensive PK substudy only. According to schedule in Table 7.
Clinical laboratory samples	X	X		X	X	X	X	X	X	X	X	Hematology, chemistry, and urinalysis.
Physical examination	X	X			X		X			X	X	
Vital signs for all participants	X	x d	X	X	X	X	X	X	X	X	X	Predose vital signs include body temperature, respiration rate, and orthostatic BP and HR.  Refer to Section 9.4.2 for further details on vital signs.

Protocol Amendment No.: 05

Table 1: Schedule of Activities for Study IM027040 (Main Study)

					Treati	ment (Da	y 1 to W	eek 26) a			Post-	
	Screening			Day 8	Day 29	Day 57	Day 85	Day 113	Day 141	Day 183	treatment	
	(Day -42 to Day -1)	Day 1	Day 2 b	Week 1 (± 3 days)	Week 4 (± 3 days)	Week 8 (± 5 days)	Week 12 (± 5 days)	Week 16 (± 5 days)	Week 20 (± 5 days)	Week 26 (+ 5 days)	follow-up c (28 ± 7 days after Week 26)	Notes
												During post-Day 1 visits, additional BP monitoring is required (similar to Day 2 visit) if either asymptomatic or symptomatic low BP criteria are met, as specified in Section 5.1.2.1.
Orthostatic evaluations				At every visit, including screening, symptoms that could indicate the presence of orthostatic intolerance, orthostatic hypotension, and orthostatic tachycardia will be gathered.  Refer to section 9.4.2 and section 5.1.2.1 further details on orthostatic evaluations.								
Serial BP and HR for participants enrolled in intensive PK substudy			See notes.									Intensive PK substudy only. According to schedule in Table 7.
Pharmacokinet	ic and Biom	arker	nrker Assessments									
Blood samples for sparse PK profiling			See notes.									According to schedule in Table 6.
Blood samples for intensive PK profiling						See	notes.					Intensive PK substudy only. According to schedule in Table 7.

930149229 6.0

Protocol Amendment No.: 05

Date: 22-Sep-2022

Approved vb.0

Table 1: Schedule of Activities for Study IM027040 (Main Study)

					Treati	ment (Da	y 1 to W	eek 26) a			Post-	

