# Day 2 blood pressure monitoring (for participants that were unable to receive evening dose on Day 1 due to having met either asymptomatic or symptomatic low BP criteria):

At the Day 2 visit, participants will receive a reduced dose of BMS-986278 (10 mg BID) while those randomized to placebo will be administered placebo for 10 mg BMS-986278 BID. Dose reduction should be appropriately noted in the case report form.

On Day 2, participants will remain at the site for at least 4 hours post dose. Orthostatic BP and HR will be performed predose and 1.5, 2, and 4 hours post dose. Participants will be carefully monitored for symptoms associated with low BP.

Participants will remain on reduced dose (10 mg BMS-986278 BID or matching placebo for 10 mg BMS-986278 BID) and will take the Day 2 evening dose at home and return to the study site on Day 8 if neither *asymptomatic* nor *symptomatic* low BP criteria are met.

If either *asymptomatic* or *symptomatic* low BP criteria, as described for Day 1, are met on Day 2, participants will be discontinued from study treatment (but continue in the study).

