#### Blood pressure monitoring at post-Day 1 study visits:

At every post-Day 1 study visit, vital signs, including orthostatic assessments, will be performed.

Participants will take the evening dose at home and will return for their next scheduled study visit, as indicated in the Schedule of Activities (Section 2), if neither asymptomatic nor symptomatic low BP criteria are met during any post-Day 1 study visit.

If either *asymptomatic* or *symptomatic* low BP criteria, as described for Day 1, are met on any post-Day 1 visit (predose), participants will remain at the site for at least 4 hours. Orthostatic BP and HR will be performed 1.5, 2, and 4 hours after the low BP criteria at predose are detected.

Participants will not receive the evening dose and will remain at the site until BP resolution criteria are met:

- a) The participant provides 2 consecutive seated BP measurements (at least 30 minutes apart) showing SBP > 85 mmHg and DBP > 55 mmHg
- b) The participant does not demonstrate orthostatic hypotension

Protocol Amendment No.: 05

c) Potential symptoms of decreased BP (as described under Day 1) have not been present for at least 30 minutes

If a decision is made to reduce to 10 mg BMS-986278 BID (or placebo for 10 mg BMS-986278 BID), the participant will return to the site the following day prior to receipt of the morning dose and will follow the Day 2 BP monitoring instructions. Dose reduction should be appropriately noted in the case report form.

Identifiable causes of low BP at any study visit, unrelated to study treatment, will be managed as clinically indicated. The management of initial low BP without an identifiable cause will include BP monitoring consistent with that described for Day 1 and Day 2.

At every post-Day 1 study visit, if any predose BP and/or HR measurements meet asymptomatic or symptomatic low BP criteria, participants will not receive study treatment during that visit.

Blood pressure monitoring criteria described above will apply to the OTE.

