## 9.4.2 Vital Signs

Predose vital signs will be collected at the timepoints provided in Schedule of Activities for the main study (Table 1) and for the OTE (Table 2), and will include body temperature, respiration rate, and orthostatic BP and HR.

During visits when orthostatic BP and HR are required (refer to Section 5.1.2.1), body temperature and respiration rate will only be required predose.

Protocol Amendment No.: 05

During orthostatic assessments, participants will be monitored for orthostatic intolerance, orthostatic hypotension, and orthostatic tachycardia, as defined in Section 5.1.2.1.

Additional serial BP and HR measurements will be collected as part of the intensive PK substudy in the main study, as shown in Table 7.

BP monitoring on Days 1 and 2 and for all subsequent study visits is described in Section 5.1.2.1.

Details for BP measurements and orthostatic assessments will be provided.

Participants who are discontinued from study treatment do not require BP monitoring and orthostatic assessments, as described in Section 5.1.2.1. Vital signs will be collected per the Schedule of Activities (Section 2).

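### For low blood pressure found before dosing at a post-Day 1 visit, Section 7.4 omits the dose hold in Section 5.1.2.1 and counts the site stay from a dose that should not be given

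*Combined protocol and SAP*

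**What the plan says.** Protocol Section 5.1.2.1, under BP monitoring at post-Day 1 visits, covers low BP detected before dosing. On the visit dose it says: "if any predose BP and/or HR measurements meet asymptomatic or symptomatic low BP criteria, participants will not receive study treatment during that visit". On the evening dose and release: "Participants will not receive the evening dose and will remain at the site until BP resolution criteria are met". The site stay is at least 4 hours, with no reference to a dose. If the dose is then reduced to 10 mg, the participant comes back the next day before the morning dose and follows the Day 2 monitoring instructions.

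Section 7.4, under post-Day 1 study visits, opens by having morning doses given at the site at every such visit. For low BP it continues: "refer to Day 1 BP monitoring in Section 5.1.2.1 for details), participants will remain at the site for at least 4 hours post dose". The next sentence reads: "Orthostatic BP and HR will be performed 1.5, 2, and 4 hours after the low BP criteria at predose are detected". It mentions a possible reduction to 10 mg and a return the next day, but not the Day 2 monitoring.

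For Day 1 itself, 7.4 writes out the evening hold and the release conditions: "participants will not receive the Day 1 evening dose and will remain at the site until", followed by the three criteria.

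**The concern.** The two sections govern the same event and do not give the same instruction. Section 5.1.2.1 withholds the dose. Section 7.4 counts the stay from a dose, which implies that one was given, and nowhere tells the site to hold it. Because 7.4 spells out the evening hold and release criteria for Day 1, a reader could take their absence from the post-Day 1 text as deliberate.

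What is at stake is participant safety. Low BP is the drug's main monitored risk: the first-in-human study (Section 3.4.4.2) found generally dose-dependent BP reductions, and Section 9.2.5 makes BP-related events adverse events of special interest. A site that uses the dosage section as its dosing instruction could give study drug to a participant who has just met low-BP criteria, for example a confirmed seated systolic BP below 85 mmHg.

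**Working it through.** The plan has no figure to reproduce here, so the check is a comparison of texts. The last column is the Day 1 part of 5.1.2.1, which is the only text that the post-Day 1 part of 7.4 cites.

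| Low BP before dosing, post-Day 1 visit | 5.1.2.1, post-Day 1 | 7.4, post-Day 1 | Day 1 text cited by 7.4 |
|---|---|---|---|
| That visit's dose | Withheld | No hold; doses given at the site | No hold; the morning dose has already been taken |
| Site stay | At least 4 hours | At least 4 hours, counted from a dose | At least 4 hours, counted from the Day 1 dose |
| Repeat BP and heart rate | 1.5, 2 and 4 hours after detection | Same | Predose, then 1.5, 2 and 4 hours after the dose |
| Evening dose | Withheld | Not mentioned | Withheld, worded for Day 1 |
| Release | When resolution criteria are met | Not mentioned | When resolution criteria are met, worded for Day 1 |
| Day after a decision to reduce | Return before the morning dose, with Day 2 monitoring | Return before the morning dose only | Not covered for later visits |

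Reading across:

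1. The visit dose is the substantive gap. The hold is in neither 7.4 nor the text that 7.4 cites. On Day 1 the event follows the morning dose, so there is no visit dose left to hold.
2. The length of stay is the only direct textual conflict. If the dose is withheld, there is no dose from which to count 4 hours.
3. The evening hold and release criteria can be reached through the cross-reference, but only by applying Day 1 wording to a later visit.
4. The repeat readings agree.

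Section 8.1 was checked as a possible remedy. For participants still on 30 mg, 60 mg or matching placebo, it requires the choice between reduction and discontinuation to be discussed with the Medical Monitor or Study Director. It says nothing about the dose due that morning. Participants already on 10 mg (or its placebo) are discontinued, which by implication settles their visit dose. The gap therefore concerns participants who have not yet been reduced.

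Scheduled post-Day 1 visits with a dose at the site (Tables 1 and 2):

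- Main study: Weeks 1, 4, 8, 12, 16 and 20 = 6.
- Optional extension: Weeks 1, 4 and 16 = 3.
- Total: 6 + 3 = 9.

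Week 26 is left out in both parts because it falls on the day after the last dose (Tables 6 and 8). Day 2 is left out because it has its own rule.

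**The case against.** The strongest reply is that this is an editorial mismatch inside a protocol that protects the participant several times over. Section 9.4.2 says "BP monitoring on Days 1 and 2 and for all subsequent study visits is described in Section 5.1.2.1", and the vital signs notes in both schedules point to 5.1.2.1 as well. The text 7.4 cites holds two of the three rules. Section 8.1 brings in the Medical Monitor or Study Director. The reference to time after dosing is probably a slip, since the following sentence of 7.4 times the readings from predose detection.

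Most of this stands. Section 5.1.2.1 can reasonably be read as governing, and apart from the length of stay the differences are gaps rather than opposite instructions. What survives is that neither 7.4, nor the text it cites, nor 8.1 states the visit-dose hold.

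Three stronger readings are tempting, and the documents do not support them:

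- A reader might infer that the participant would take a full day's assigned dose and be released as the BP effect peaks, since reductions generally reached their maximum 4 to 8 hours after dosing. That requires a site to miss 5.1.2.1 and also bypass 8.1. Four hours is a minimum stay, and the same minimum applies on Day 1, so release near the start of that window is not peculiar to 7.4. The first-in-human reductions were also reversible and mostly asymptomatic.
- A reader might infer that 7.4 removes the evening hold and resolution criteria altogether. It does not repeat them for these visits, but its cross-reference leads to them in Day 1 form.
- The Table 1 note says "During post-Day 1 visits, additional BP monitoring is required (similar to Day 2 visit) if either", and on Day 2 a dose is given: "At the Day 2 visit, participants will receive a reduced dose of BMS-986278 (10 mg BID"). A reader might infer dosing from the comparison. The note likens the monitoring to Day 2, not the dosing, and goes on to cite 5.1.2.1.

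**Conclusion.** The inconsistency is real and should be corrected. Followed alone, 7.4 leads to the wrong action on the visit dose at up to 9 scheduled visits per participant. Nine is a maximum: it assumes that the participant stays on treatment throughout and enters the optional extension.

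The documents give no rate of predose low BP at these visits, so the number of participants affected is not estimated. The risk depends on a site using 7.4 without 5.1.2.1, and how often that would happen is also unknown. No effect on the primary analysis, type I error or power is claimed.

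The intended policy is not in doubt. The current text of 5.1.2.1 states the hold outright, and the change history for Revised Protocol 01 records that it was added to that section on purpose. This is a question of internal consistency, not of design.

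**What to change.** In Section 7.4, post-Day 1 study visits, make three changes:

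1. Replace the sentence on the site stay, deleting its reference to time after dosing, with wording such as: *If asymptomatic or symptomatic low BP criteria are met predose, no study treatment is given at that visit and the evening dose is withheld. The participant stays on site for a minimum of 4 hours and until the BP resolution criteria are met (see BP monitoring at post-Day 1 study visits in Section 5.1.2.1).* The word *predose* matters, because the visit-dose hold in 5.1.2.1 is triggered by predose measurements.
2. Leave the sentence on the 1.5, 2 and 4 hour readings as it is.
3. Add that, after a decision to reduce to 10 mg or its placebo, the participant follows the Day 2 BP monitoring instructions on the next day.

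The cost is a wording edit in one section, which an administrative letter or the next amendment can carry. It adds no visits, assessments or participants, and it sets no new treatment policy because 5.1.2.1 already contains every rule.

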## 7.5 Investigational Product Handling/Storage/Accountability

The IP should be stored in a secure area according to local regulations. It is the responsibility of the investigator, or designee where permitted, to ensure that IP is only dispensed to study participants. The IP must be dispensed only from official study sites by authorized personnel according to local regulations.

The product storage manager should ensure that the IP is stored in accordance with the environmental conditions (temperature, light, and humidity) as determined by BMS. If concerns regarding the quality or appearance of the IP arise, the IP should not be dispensed, and BMS must be contacted immediately.

Study intervention not supplied by BMS will be stored in accordance with the package insert.

IP documentation (whether supplied by BMS or not) must be maintained that includes all processes required to ensure drug is accurately administered. This includes documentation of drug storage,

Protocol Amendment No.: 05

administration and, as applicable, storage temperatures, reconstitution, and use of required processes (eg, required diluents, administration sets).

• Further guidance and information for final disposition of unused study treatment are provided in APPENDIX 2.

#### 7.5.1 Retained Samples for Bioavailability/Bioequivalence

Not applicable.

### 7.6 Treatment Compliance

At each protocol-scheduled visit from Day 29 (Week 4) to Week 26 (as shown in Table 1 for the main study and Table 2 for the OTE) and at the time of dose reduction or dose discontinuation (if applicable), treatment compliance will be evaluated for each participant by comparing the number of tablets taken by the participant with the number of tablets planned. Percentage compliance will be calculated as follows:

% compliance = (number of tablets taken  $\div$  number of tablets planned)  $\times$  100

If the estimated treatment compliance falls below 90%, the participant must be retrained at the site on study treatment administration.

Participant Study Medication diaries will be used by participants to record study treatment administration. Dosing diaries that have been completed should be reviewed at each study visit.

## 7.7 Concomitant Therapy

For the PF-ILD cohort, mycophenolate mofetil, mycophenolic acid, azathioprine or and/or tacrolimus are permitted only if the participant is on a stable dose at least 6 months prior to screening. These immunosuppressive medications cannot be initiated during the course of the main study.

Although pirfenidone or nintedanib are allowed during the main study for both cohorts, they are not allowed in combination with one another during the main study.

Stable DMARDs used to manage synovitis in rheumatoid arthritis patients will be permitted, as long as these agents have been in place and stable for at least 6 months prior to screening. DMARDs include, but are not limited to, hydroxychloroquine, sulfasalazine, anti-TNF alpha antagonists, interleukin antagonists, abatacept, tofacitinib, and baricitinib.

During the OTE, modifications and initiation of DMARD use are allowed per clinician discretion or patient preference.

